#### 5.1 Acamprosate for relapse prevention in alcohol dependence

NICE recommends the use of acamprosate in combination with a psychological intervention as first-line treatments for relapse prevention in moderate to severe alcohol dependence (13). Acamprosate Calcium has been licensed for use in relapse prevention in alcohol dependence in the UK since 1995. Acamprosate is believed to modulate the glutamatergic system and stabilise the imbalance between inhibitory (GABA) and excitatory (glutamate) neurotransmitters in the brain consequent to the adaptations to chronic alcohol exposure thus reducing the conditioned effect of alcohol and the negative reinforcement of the addictive behaviour (14-16). Systematic reviews of the effectiveness of acamprosate found it to have a significant but moderate effect on maintenance of alcohol abstinence in clients with alcohol dependence (16, 17).

#### 5.2 Adherence to acamprosate

Despite the therapeutic potential of acamprosate, adherence to the medication poses a problem for effectiveness in clinical practice. Medication adherence is a common problem across clinical care but is particularly an issue in chronic conditions and greater risk of poor adherence has been associated with substance misuse [32]. A meta-analysis of the effects of compliance on the efficacy of acamprosate in alcohol dependence found low rates of compliance (18), 69% of participants were at least 80% compliant from treatment initiation to the first post-baseline appointment at 15-30 days (early compliance) and 51% of participants were at least 80% compliant between the first post-baseline appointment to the end of treatment (late compliance). Examining the adherence rates to acamprosate of those clinical trials identified in the systematic review conducted by Donoghue et al., (19) (table 1) a wide variation between studies was identified, ranging from 28% up to 6 months in the only UK trial (20) to 94% in Portugal (21).

Several methods are used in clinical trials to monitor medication adherence. Swift et al., (22) suggest a hierarchy from low to high confidence in the method of adherence monitoring for

naltrexone based on a patient's ability to evade measurement of adherence. Patient self-report, counting of returned medication or inspection of blister packs were assigned "low" confidence, electronic monitoring of pill bottle opening (Medication Events Monitoring System (MEMS) caps) or biomarkers such as the addition of riboflavin were assigned a "medium" confidence. "High" confidence was assigned to supervised dosing, long-acting injectable preparations or monitoring of blood levels of the prescribed medication. Similar methods of adherence monitoring have been used in clinical trials for acamprosate (see Rösner et al., (16) for a review). In clinical practice some methods of adherence monitoring, such as supervised dosing and monitoring blood levels, may not be practical due to staff time, costs and practicality for service users, a combination of methods may therefore be advantageous. Further, no injectable preparation of acamprosate has been developed.

Suboptimal outcomes may result from underdosing, overdosing or taking medication at incorrect intervals (23). The impact of medication adherence on treatment effectiveness has been explored in several naltrexone trials for alcohol dependence. Results suggest better medication adherence is associated with improved outcomes (24-30). There has been comparably less work completed investigating the effect of adherence to acamprosate on alcohol outcomes. A recent analysis of the COMBINE study data found that poor adherence to both acamprosate and naltrexone was associated with lower percentage days abstinent and higher percent days heavy drinking (31). It was also found that those who were non-adherent early in the trial had poorer alcohol outcomes than those who were non-adherent later in the trial regardless of the medication prescribed.

### 5.3 Reasons for non-adherence

The reasons for non-adherence are complex and often due to multiple influences (32). The complexity of the dose regimen may influence adherence to medication with greater dose frequency and complexity of instructions associated with poorer adherence (33, 34). Comorbid depression is a predictor of poor adherence to prescribed medical treatments in those with chronic health conditions such as HIV and AIDS (35), diabetes (36) and coronary heart disease. Depression is common in patients with alcohol dependence (37) and may therefore be a contributing factor to poor adherence to pharmacotherapies for relapse prevention.

The experience of side-effects may contribute to non-adherence to medication for alcohol relapse prevention. Side-effects were the second most common reason for medication non-adherence (behind forgetting) in the COMBINE study of naltrexone and acamprosate (31). The combined therapy of acamprosate and naltrexone resulted in decreased adherence (defined as taking 80% or more of prescribed medication) compared to a single active therapy. It was reported that this may be due to the increase in side effects experienced by participants taking both medications (30). In addition, those who did not adhere to medication reported not only more side-effects but also a lack of benefit from the medication (31).

The Self-regulatory model (SRM) was conceptualised by Leventhal et al. (38) to help to explain illness related behaviour, including adherence to medications, in chronic illness. In the SRM a person's cognitive representation of their illness is associated with their subsequent coping behaviour, including adherence to medication. The model suggests that the person is an active 'problem solver' and their coping behaviour represents a common sense response to their interpretation of their experience and knowledge of their illness. Horne (39) expanded this model to explain treatment adherence to include specific treatment beliefs. It is proposed that patients' adherence decisions are based on an assessment of the costs and benefits (40). A person's beliefs about the necessity of the medication for improving or maintaining their health are weighed against

the person's concerns about the potential adverse effects of the medication. In chronic health conditions such as asthma, diabetes, cardiac disease and cancer, a greater perception of the benefits of a medication is associated with greater adherence, and greater concern about adverse effects of a medication is associated with poorer adherence (40, 41). The development of effective interventions to improve patients' uncertainties about the necessity for medication and concerns about the potential adverse effects is a priority to enhance adherence in chronic health conditions (23, 41)

#### 5.4 Medication management

The NICE alcohol treatment guidelines (13) recommend that service users prescribed acamprostate or naltrexone "...should stay under supervision, at least monthly, for 6 months, and at reduced but regular intervals if the drug is continued after 6 months" p456. In NHS clinical practice the frequency and content of support is delivered by a combination of different agencies including primary care and specialist alcohol services.

Psychosocial interventions to support improved adherence to pharmacotherapies for alcohol dependence have the potential to promote positive beliefs about medication and address concerns. BRENDA is a manualised intervention (42) designed for use by health care professionals and has been used in several clinical trials (43-46). BRENDA is a 6 stage intervention and is an acronym for these stages; Biopsychosocial evaluation, Report, Empathy, Needs assessment/goals, Direct advice, and Assessment. BRENDA has been found to be beneficial for improving adherence to naltrexone for alcohol dependence (47).

Medical Management is a manual based psychosocial intervention that was developed from BRENDA and other available MM interventions by Pettinati et al., (48) for the COMBINE study of naltrexone and acamprostate for alcohol dependence (24) and has been used in subsequent clinical trials of other medications (49, 50). Medical management aims to improve medication and psychosocial treatment adherence by providing education, support and practical advice to service users about their drinking behaviour and medication. The initial session lasts approximately 40-60 minutes, which acts as a foundation for the subsequent sessions which last approximately 15 to 30 minutes. The initial session includes information about the patient's diagnosis, identifies treatment goals, the rationale for taking the prescribed medication, information about the medication and a review of the dosing instructions, the rationale for adhering to the prescribed dose regimen and developing an individualised plan for maintaining adherence and discussing support groups participation. Alongside the calls, the participant will receive four summary letters over the 6 month period. The summary letters provide a visual reminder of the aims, goals and key information regarding their medication management plan. Despite the successful inclusion of psychosocial intervention to enhance adherence in clinical trials, there has been little research into its application in a more typical clinical setting.

#### 5.5 The role of the pharmacist

There has been an increasing focus on the extension of the pharmacist's role beyond medication dispensing to improve public health (51-53), including their established role in HIV prevention in opioid addiction (54, 55), medicines use reviews (56) and supporting medicines adherence (57, 58). The delivery of MM to improve adherence to relapse prevention medication for alcohol dependence complements the expanding role of the pharmacy. In 2011 the Royal College of General Practitioners and the Royal Pharmaceutical Society issued a joint statement which identified a role for suitably qualified pharmacists to contribute to care planning and treatment interventions

in substance misuse (59). This has been followed by a recent report of the commission on the future models of NHS care delivered through pharmacy (60).

The Healthy Living Pharmacy (HLP) initiative recognises the significant role that community pharmacists should play in the reduction of health inequalities (61). HLP's have been successful and the initiative is currently being rolled out across the UK. Alcohol misuse is one of the conditions targeted by the HLP. Prior research has found that pharmacists and support staff have positive attitudes towards providing extended services in alcohol and substance misuse when adequate training is provided (62, 63) and alcohol service users are willing to engage with the pharmacists for this role, viewing the pharmacy as an accessible and suitable place to discuss issues related to alcohol (64). There has also been an increased emphasis on more specialist pharmacist providing support via a central telephone support service for more complex health conditions, providing patients with access to pharmacists with greater expertise and with greater convenience than attending a local community pharmacy (65).

### 5.6 Contingency management

Engagement with psychological interventions and retention in treatment is often poor in alcohol dependence and is associated with poorer treatment outcome (66, 67). CM is based on the psychological theory of operant conditioning. Target behaviours (for example, attendance at therapy sessions, medication adherence, or abstinence from alcohol) are reinforced by consistently applying small rewards in the form of vouchers, money or prizes, when the target behaviour is achieved. There is a growing body of work using CM in the substance misuse field, showing improved treatment retention and engagement (47) as well as adherence to prescribed pharmacotherapies such as naltrexone for opiate relapse prevention, and improved uptake rates of hepatitis vaccination, tuberculosis screening and treatment, and adherence to prescribed HIV pharmacotherapy (68-70). A systematic review conducted by NICE (13) concluded that the research on CM in alcohol dependence is limited and recommended the need for further research in this area based on the compelling evidence in the substance misuse field (69). Three randomised controlled trials (47, 71, 72) for the effectiveness of CM in alcohol dependence treatment were identified by a systematic review conducted by NICE (13). All of these studies used a prize-based protocol with incentives of variable magnitude based on abstinence and/or treatment participation (47, 71, 72). Fixed monetary incentives or monetary incentives on an escalating scale may also be used, for example to improve tuberculosis treatment adherence in injecting opioid and cocaine users (73) and improving the number of doses of naltrexone taken in those with opiate dependence (74). Much of the literature on CM has been conducted in the US. However, recognition for the therapeutic potential of CM is growing in the UK. A UK NIHR programme grant on CM in substance misuse, of which JS is the chief investigator, has found significant effects of CM on hepatitis B vaccination adherence and completion in injecting drug misusers (n=210) (75). Vaccination completion was just 9% in the treatment as usual group but significantly higher completion rates were found for both an escalating monetary incentive (49%), which began at £5 and increased by £5 after each completed vaccination and a fixed monetary incentive (45%) of £10 per completed vaccination.

### 5.7 Why this research is needed now

Alcohol dependence is a chronic condition and relapse is common following conventional psychosocial interventions (11, 12). The effectiveness of acamprosate in conjunction with psychosocial therapies for relapse prevention in alcohol dependence has been well documented (13,

16) such that routine prescribing of acamprosate in alcohol dependence in NHS services is recommended by NICE [6]. Its use in the UK has doubled between 2003 and 2012, including an 11% increase since publication of the NICE guidelines (76). Despite this, the impact of acamprosate is restricted due to poor adherence and insufficient duration of use. Supporting patients in using acamprosate correctly by providing education about the benefits of acamprosate, its role in relapse prevention and possible side effects, and practical advice and support through the application of MM, has the potential to help improve adherence and increase the clinical effectiveness of acamprosate. However at present there is insufficient evidence as to which forms of intervention are effective in increasing acamprosate adherence to guide clinical practice. Hence, clinical trials of strategies to increase relapse prevention medication adherence were prioritised as a research recommendation by NICE (13).

The delivery of MM by pharmacists fits the framework for development and expansion of the role of the pharmacy proposed in the Royal Pharmaceutical Society's recent report (60) and also the HLP initiative. Pharmacists are ideally placed to deliver MM in this context. However the effectiveness of interventions to increase medication adherence for alcohol dependence delivered by pharmacists is currently not known.

CM has proven effectiveness to promote medication adherence in substance misuse, with adoption into NICE guidance and clinical practice in the UK (69). CM can be delivered at relatively low cost and without extensive training compared to other psychological and behavioural interventions (such as cognitive behaviour therapy or motivational enhancement therapy) but with greater clinical effectiveness in substance misuse. Financial incentives in CM are relatively modest (typically less than £10 per session) and can be delivered by staff with less training and clinical skill than required for other psychological interventions used in alcohol dependence, as the intervention follows a simple behavioural reinforcement schedule. There is currently a small but growing evidence base for CM in alcohol dependence, but if shown to be effective it has considerable potential to be adopted within NHS services and the pharmacy to enhance alcohol dependence treatment.

## **6. Aims and objectives**

Aim:

1. To evaluate the acceptability, effectiveness and cost-effectiveness of adjunctive MM with and without CM in improving adherence to acamprosate for relapse prevention in alcohol dependence.

Objectives:

- I. To conduct an internal pilot study to assess the feasibility, recruitment and acceptability of the proposed MM and CM interventions for pharmacists and service users.
- II. To conduct a definitive three-arm, randomised controlled trial of the effectiveness of MM with and without CM compared to SS alone in enhancing adherence to acamprosate in alcohol dependence relapse prevention.
- III. To estimate the cost effectiveness of MM with and without CM compared to SS alone in enhancing adherence to acamprosate in alcohol dependence relapse prevention.
- IV. To assess the impact of adherence to acamprosate for alcohol dependence relapse prevention on abstinence and reduced alcohol consumption.

Primary effectiveness and cost-effectiveness hypotheses:

- MM and MM+CM will be more effective than SS alone in terms of the percentage of prescribed acamprosate taken, measured using the medication events monitoring system, supplemented by pill count and self-report at 6 months post-randomisation.
- MM and MM+CM will be more cost-effective than SS alone at 12 months post-randomisation.

Secondary hypotheses:

- MM and MM+CM will be more effective than SS in terms of the percentage of prescribed medication taken, measured using the medication events monitoring system, supplemented by pill count and self-report, at 12 months post-randomisation.
- Greater adherence to acamprosate will be associated with improved alcohol outcomes, namely a higher percentage of days abstinent, less units of alcohol per drinking day, longer time (latency) to first alcoholic drink, reduced relapse to any drinking and reduced relapse to heavy drinking at 6 and 12 months post-randomisation.
- Service user beliefs about medication, and therapeutic relationship with care providers, will moderate medication adherence at 6, and 12 months post-randomisation.

## **7. Method**

### 7.1 Internal Pilot

An internal pilot phase will be conducted to demonstrate that recruitment, randomisation, the MM and CM interventions run as planned. This will include the practicability of recruiting of, on average, 11 participants per study site per month and delivery of MM and CM in by pharmacists based in a central telephone support service. The pilot phase design and methodology will be identical to the full trial. This will allow data collected during the pilot phase to be included in the statistical analysis of the primary and secondary outcomes after completion of the full trial as an internal pilot. This approach has been chosen as it is more cost effective and suitable for the proposed research. If the recruitment target is met and the trial proceeds, the participants in the pilot phase will be included in the final analysis, so maximising recruitment potential from the sites.

#### 7.1.1 Design and theoretical/conceptual framework

The study will be a 3-arm, pragmatic, randomised controlled, parallel group clinical trial. Each participant will be prescribed acamprosate as soon as possible after alcohol abstinence is achieved for a minimum duration of 24 weeks. Follow-up contacts with the research team will take place 6 (+30 days) and 12 (+60 days) months post randomisation. Participants will collect their medication monthly from the community pharmacy, which will be dispensed from designated pharmacies in bottles with MEMSCaps. Consented participants will be randomised (in the order of 2:1:1) to receive;

- SS consisting of monthly pick up of prescribed acamprosate from the community pharmacy and monthly follow-up with their specialist alcohol team for three months followed by monthly follow up with their GP for three months; or
- SS+ MM once a week for the first 6 weeks, reducing to once a fortnight for the following 6 weeks, and then monthly for 3 months, delivered by telephone by a trained pharmacist from a central telephone support service; or
- SS+MM+CM which will include incentivisation for completion of each of the telephone MM support sessions, with the pharmacist.

#### *7.1.1.1 Treatment arm 1: Standard support (SS)*

All participants in the trial will be prescribed acamprosate (two 333mg tablets morning, afternoon and evening or two 333mg tablets in the morning and one 333mg tablet in the afternoon and evening if the service users body weight is below 60kg) as soon as possible following alcohol abstinence in addition to the psychosocial care normally provided. The decision to initiate acamprosate will be determined by the treating clinician in the specialist alcohol service in conjunction with the service user.

The NICE guideline on diagnosis, assessment and management of harmful drinking and alcohol dependence (13) recommends, "Service users taking acamprosate should stay under supervision, at least monthly, for 6 months, and at reduced but regular intervals if the drug is continued after 6 months" p426. In clinical practice, after completion of assisted alcohol withdrawal, service users remain under the care of the specialist alcohol service for up to three months before they are transferred back to the care of their GP for ongoing care including prescribing. The type, frequency and intensity of psychosocial intervention received vary between specialist alcohol services and between individual service users, dependent on their needs, local funding and services available. As this is a pragmatic RCT, SS will be the care normally provided by local participating services, and service use will be recorded for each participant. However, participating services have agreed to follow the NICE guideline with respect to acamprosate prescribing with trial participants. Based on the current service provision of the five proposed study centres, SS is monthly pick up of prescribed acamprosate from the community pharmacy and monthly monitoring of the service user for three months by the specialist alcohol service and then returned to the care of their GP for monthly monitoring in accordance with the NICE guidelines (13) and current NHS clinical practice. As the trial is pragmatic it will be possible for patients to continue being prescribed acamprosate beyond the 24 week period of medication adherence monitoring providing this is agreed between patients and clinicians, in accordance with NICE guidelines.

#### *7.1.1.2 Treatment arm 2: Standard support plus medication management (SS+MM)*

Participants will follow the same care pathway as those in the SS arm of the trial with the addition of MM, which will be delivered by a central telephone support service by trained pharmacists. The MM intervention will be adapted from the Medical Management intervention developed by Pettinati (48) for the COMBINE study, a randomised controlled clinical trial of naltrexone and acamprosate for alcohol dependence. A freely available comprehensive manual has been published by the research group. This will be used as a basis for the MM intervention for the proposed research. Adaptation has been made in consultation with service users and pharmacists to ensure that it is suitable and acceptable in the context of a UK central pharmacy telephone support service, delivered by trained pharmacists.

Medical Management in the COMBINE study was delivered once a week for the first 6 weeks, reducing to once a fortnight for the following 6 weeks, and then monthly for three months. The current study will follow the same schedule and the MM will be delivered by telephone by a trained pharmacist based in a central telephone support service in the UK provided by Celesio. The initial MM session will last approximately 30-45 minutes and will act as a foundation for the subsequent sessions, which will last approximately 10-15 minutes each. Each participant will be assigned a specific pharmacist based in the central telephone support service who will deliver each of the MM sessions for that participant where possible. The pharmacist will call the participant to deliver the

MM session at an agreed time and a text message reminder will be sent the day before the appointment.

MM will provide support in developing strategies to help participants to manage their medication including the rationale for taking acamprosate, adhering to the dose regimen and managing side effects, education about their medication and alcohol dependence, and supporting participants' efforts to change their drinking behaviours. Treatment goals will be identified to tailor the intervention to the participant and an individual plan for maintaining adherence will be developed with the participant in the initial session to guide successive MM sessions. Over the 6 month period the pharmacist will send four summary letters to the participant highlighting the participant's individual aims, goals and key information regarding their medication management plan.

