#### *7.1.1.3 Treatment arm 3: Standard support plus medication management with contingency management (SS+MM+CM)*

Although available evidence suggests that MM enhances adherence to prescribed medication for relapse prevention in alcohol dependence, there is concern that attendance at MM sessions may be sub-optimal (77). To optimise attendance, participants will follow the same care pathway as those in the SS+MM arm of the trial but with the addition of CM. Incentives in the form of vouchers (not redeemable for alcohol) will be provided to reinforce attendance at MM sessions by telephone with the pharmacist. The CM procedure and value of the incentives has been informed by the available literature on CM in substance misusers (69) and alcohol dependence (13) and focus groups with service users with experience with treatment services for alcohol dependence. Participants will receive between £2 and £10 in the form of a voucher for each MM session completed, with a total value of up to £120 for completing all support sessions. After each MM session a SMS text message will be sent to the participant to inform them that they have been awarded a voucher, the magnitude of the voucher and the total voucher value received to date.

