#### 7.2.2 Sample size

A clinically important difference in adherence to medication is estimated as an effect size of the order of 0.3. A recent meta-analysis (92) identified a larger effect size for acamprosate versus placebo when converted to drinking outcomes of the order of 0.4, with a number of studies reporting larger effects. In addition a major issue mediating the potential effect of acamprosate relates to adherence with very low rates reported in UK trials. This effect translates to what is considered a clinically important difference in mental health interventions in terms of a numbers needed to treat of 8, in that if any intervention strategy is found to be superior 8 participants would need to be treated to create an additional participant who is abstinent. As with all pragmatic studies final interpretation will be based upon actual effects observed and the integration of economic outcomes, but an effect size of less than 0.3 is unlikely to be clinically important.

To estimate this difference using power of 80%, alpha 0.05 with a 2 sided tested and differential allocation of 2:1:1 requires 524 analysed at the primary end-point, 6 months across the three groups. Allowing for attrition of 30%, less than observed in other trials in similar populations, requires a total sample size at allocation of 748; 374 allocated to SS, and 187 to SS+MM and 187 to SS+MM+CM. In addition to addressing the primary outcome the sample size is sufficient to identify a

clinically important difference effect size of 0.3 in alcohol consumption measures at 6 and 12 months post-randomisation.

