### 7.2.4 Data analysis

In the main trial the primary outcome measure is percent prescribed medication taken at 24 weeks post-randomisation assessed using a triangulation method. After checking for distributional assumptions and employing necessary transformations, an initial multiple analysis of covariance will be undertaken using a mixed model approach addressing the observed differences between SS versus SS+MM versus SS+MM+CM. If this analysis provides evidence of effect a second analysis of covariance will explore the differences of SS versus SS+MM and SS versus SS+MM+CM. Covariates included in the analysis will include stratification variables, gender and body weight (<60kg or 60+ kg). Mean differences between the groups will be presented with associated 95% confidence intervals. Multiple imputation will be employed to address the nature of missing data and sensitivity analysis will address the influence of missing data on the observed outcome. Secondary analysis will address drinking outcomes at 6 and 12 months using appropriate modelling approaches and these will be adjusted for known confounders; SADQ, site, age and gender. Time to relapse and relapse to heavy drinking will be assessed using survival analysis. Further secondary analyses will explore adherence data at 12 months. We will explore the association between adherence and drinking outcomes using a linear regression adjusted for known confounders and include an adherence\*allocation interaction term. As with most trials the analysis plan will be refined throughout the course of the study and the final analysis plan prepared and agreed by the research team and Trial Steering Committee.

Further analysis will be conducted to identify interactions between variables, including ratings of therapeutic relationship, and fidelity of MM and CM delivery, on clinical and adherence outcomes. The analysis will be governed by an explicit data analysis plan agreed in advance by the Trial Steering Committee.

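### The 524-patient sample size makes no allowance for clustering by pharmacist in the two medication management arms, and the planned mixed model names no pharmacist effect

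*Protocol*

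**What the plan says.** **Delivery.** Protocol 7.1.1.2 allocates each SS+MM participant to a particular pharmacist: "Each participant will be assigned a specific pharmacist based in the central telephone support service who will deliver each of the MM sessions". The sentence ends with a qualifier: "who will deliver each of the MM sessions for that participant where possible". Section 7.1.1.3 extends this to the third arm: "participants will follow the same care pathway as those in the SS+MM arm of the trial but with the addition of CM". SS (7.1.1.1) consists of routine monthly pick-up and monitoring, with no MM pharmacist.

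**Sample size.** Section 7.2.2 sets the target: "A clinically important difference in adherence to medication is estimated as an effect size of the order of 0.3". It continues: "To estimate this difference using power of 80%, alpha 0.05 with a 2 sided tested and differential allocation of 2:1:1 requires 524 analysed", and then "Allowing for attrition of 30%, less than observed in other trials in similar populations, requires a total sample size at allocation of 748". It mentions no ICC, number of pharmacists, caseload or design effect. The same section says the sample is also enough for alcohol consumption measures at 6 and 12 months.

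**Model.** Section 7.2.4 says "an initial multiple analysis of covariance will be undertaken using a mixed model approach", and "Covariates included in the analysis will include stratification variables, gender and body weight". The random effects are not named. The final analysis plan is left to a later document, which was not available for this review.

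**The concern.** MM is tailored to the individual: section 7.1.1.2 describes personal treatment goals, an individual adherence plan and four summary letters. If some pharmacists are better at it than others, participants who share a pharmacist will have correlated adherence. That correlation arises in the two MM arms and not in SS.

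The protocol itself treats the pharmacist as a possible source of variation. Section 7.1.11 stratifies the fidelity sample by pharmacist and will examine how fidelity affects adherence. Section 7.1.10.2 measures the therapeutic relationship as a process measure for adherence and outcome. A sample size with no allowance for the person delivering the intervention sits awkwardly beside these plans.

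Two things are at stake. One is whether the stated 80% power can be relied on. The other is whether the intervals for SS versus each MM arm will reflect all the variation present, which depends on a model term the protocol does not specify.

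**Working it through.** **Inputs from the protocol (7.2.2).** Standardised difference 0.3 (SD = 1), two-sided alpha 0.05, power 80%, allocation 2:1:1, attrition 30%, 524 analysed, 748 randomised.

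**Inputs assumed.** Pharmacists per MM arm k = 3, 5, 10 or 20, with equal caseloads; ICC = 0.01, 0.02 or 0.05. The protocol gives neither quantity.

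**Step 1: reproduce the stated figure.** With twice as many in SS as in one MM arm and independent participants:

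n(SS) = (1 + 2) × (1.960 + 0.8416)² / 0.3² = 3 × 7.849 / 0.09 = 261.6, so 262 in SS and 131 in each MM arm.

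Total = 262 + 131 + 131 = 524, as stated. Power = Φ(0.3 / √(1/262 + 1/131) − 1.96) = 80.1%. For attrition, 524 / 0.7 = 748.6 against 748 stated, which agrees to rounding. The figure therefore carries a design effect of 1.

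**Step 2: allow for clustering in the MM arm only.**

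- Design effect: DE = 1 + (131/k − 1) × ICC
- Standard error: SE = √(1/262 + DE/131)
- Power = Φ(0.3/SE − 1.96)

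Example with k = 5 and ICC = 0.02: caseload 131/5 = 26.2; DE = 1 + 25.2 × 0.02 = 1.504; SE = √(0.003817 + 0.011481) = 0.1237; power = Φ(2.425 − 1.96) = 67.9%.

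Power at 524 analysed:

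| ICC | k = 3 | k = 5 | k = 10 | k = 20 |
|---|---|---|---|---|
| 0 | 80.1% | 80.1% | 80.1% | 80.1% |
| 0.01 | 69.6% | 73.7% | 76.9% | 78.6% |
| 0.02 | 61.0% | 67.9% | 73.9% | 77.2% |
| 0.05 | 43.7% | 54.3% | 65.8% | 73.1% |

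**Step 3: effect on the standard error if no pharmacist term is fitted.** True SE divided by the SE that assumes independence:

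| ICC | k = 3 | k = 5 | k = 10 | k = 20 |
|---|---|---|---|---|
| 0.01 | 1.13 | 1.08 | 1.04 | 1.02 |
| 0.02 | 1.25 | 1.16 | 1.08 | 1.04 |
| 0.05 | 1.56 | 1.36 | 1.19 | 1.09 |

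**Step 4: why adding participants is a poor remedy when pharmacists are few.** For 80% power the variance of the difference must not exceed (0.3/2.8016)² = 0.01147. With k fixed, the pharmacist component ICC/k does not shrink as participants are added. At ICC 0.05 and k = 3 it is 0.05/3 = 0.0167, already above the limit, so no sample size reaches 80%. At ICC 0.02 and k = 5 the requirement is 796 analysed.

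The calculation uses normal quantiles, so it is somewhat optimistic for very few pharmacists. If the same pharmacists serve both MM arms, which the protocol does not say, the per-arm caseload still applies to each comparison with SS.

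**The case against.** **The model.** A reader might infer that the primary analysis treats participants as independent and that its confidence intervals are too narrow. The text does not support that. Section 7.2.4 plans a mixed model, leaves its random effects open and defers the final plan. A list of covariates is not a list of random effects. Narrow intervals follow only if no pharmacist term is fitted and the ICC exceeds zero. This part of the objection stands.

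**The nesting.** A reader might also infer that each participant is strictly tied to one pharmacist. The protocol qualifies this, and the extent of crossover between pharmacists is unknown. Crossover would weaken the clustering, but assignment to one pharmacist remains the rule.

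**Limits on pharmacist variation.** Delivery is based on a published manual (7.1.1.2), with study-specific training (7.1.1.4) and fidelity feedback (7.1.11). These may keep the ICC low, but they do not show that it is zero. With 20 pharmacists and ICC 0.01 the loss is only about 1.5 points.

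**The number analysed.** Section 1 specifies intention to treat, 7.1.10.1 scores periods with all measures missing as non-adherent, and 7.2.4 adds multiple imputation. If all 374 and 187 were analysed, the same formula with 4 to 10 pharmacists gives 84–89% at ICC 0.01 and 75–85% at ICC 0.02. So it is not established that the trial will fall below 80%. Against that, scoring missing periods as non-adherent could dilute the effect. The point is confined to the protocol's own statement about 524 analysed.

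**False positives.** Turning the SE ratios directly into pairwise error rates would overstate them, because pairwise tests follow only if the three-arm test shows an effect. A simulation under the global null assumed a 5% gate, no pharmacist term and 4 to 10 pharmacists. Per-comparison rejection was 3.1–4.3% at ICC 0.01, 3.8–6.4% at 0.02 and about 6–13% at 0.05, against 2.4% at ICC zero. Clustering still inflates the rate, but at ICC 0.01 it stays below 5%. The gate protects less if one MM arm truly works.

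**Conclusion.** The point holds for the sample size and conditionally for the model. The stated 80% power at 524 analysed has no clustering allowance and is overstated for any pharmacist ICC above zero. Over the assumed 3 to 20 pharmacists per MM arm, the shortfall runs from about 1.5 points (78.6%; ICC 0.01, 20 pharmacists) to about 36 points (43.7%; ICC 0.05, 3 pharmacists). A single central telephone service is compatible with a small team and large caseloads, but the protocol does not say, so no one cell of the table can be called the right one.

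For the analysis, the defect is an unspecified term rather than a wrong one. If the final model omits it and the ICC is 0.01 to 0.02, the standard errors against SS would need to be about 2% to 25% larger. The correction is worth making: the missing allowance is certain, while its size is not.

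**What to change.** - **Section 7.2.2:** state the expected number of MM pharmacists and the caseload per arm, and restate power over a range of ICC values, including for the alcohol consumption measures. No increase in enrolment is proposed.
- **Section 7.2.4 (carried into the analysis plan):** name a pharmacist random effect that applies only in the two MM arms, with each SS participant as a singleton, use a small-sample degrees-of-freedom correction, and report the estimated ICC. If there are too few pharmacists to estimate it, make this a sensitivity analysis and show results by pharmacist. State how participants seen by more than one pharmacist are classified, for example by assigned pharmacist.
- **Data:** make sure pharmacist identity reaches the analysis data set. It must be known for assignment (7.1.1.2) and for stratifying the fidelity sample (7.1.11), but the description of the patient management system in section 8 does not say that it is stored there.

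The cost is wording and one recorded variable, with slightly wider intervals and a less favourable power figure.
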